8. SAFETY ANALYSES

Details of the planned displays including the population to be used for each display are presented in [Appendix 10](#) List of Data Displays.

The estimand is the effect of actual treatment in the population of participants who were randomized and dosed. All collected data will be included in reporting as described below. If a participant received the incorrect meal or formulation, data will be reported according to the actual meal and formulation received. If a participant consumed <90% of the meal, data will still be reported according to that meal. If a participant was non-compliant with OMP dosing, data will still be reported according to the OMP-containing treatment. Non-recorded missing data following study withdrawal will not be imputed.

All safety data displays will be split by actual treatment received, except where specified below.

8.1. Adverse Events Analyses

Adverse events analyses including the analysis of AEs, SAEs and other significant AEs will be based on GSK Core Data Standards.

8.2. Clinical Laboratory Analyses

Laboratory displays including chemistry laboratory tests, hematology laboratory tests, urinalysis, and liver function tests will be based on GSK Core Data Standards.

Summaries will include Screening and baseline (see [Section 5.2](#) Baseline Definitions) values, and raw and change from baseline values at the Follow-up visit, and will be split by Part and Group.

Laboratory data from eligibility screening (follicle stimulating hormone, oestradiol, human immunodeficiency virus, hepatitis B & hepatitis C) will not be reported.

8.3. Other Safety Analyses

The analyses of non-laboratory safety test results including ECGs and vital signs will be based on GSK Core Data Standards, unless otherwise specified.

10. APPENDICES

10.1. Appendix 1: Protocol Deviation Management

PDs will be tracked by the study team throughout the conduct of the study in accordance with the Protocol Deviation Management Plan (PDMP) for the study:

- PICTS database is not being used to collect protocol deviations occurring in the study. A PD spreadsheet (PD Log) is being used to collect all deviations from the protocol and is being managed by the IQVIA Clinical Research Associate.
- Every time there is a deviation, an email is sent to the GSK study team to confirm whether it should be classified as important or not, and subsequently updated in the spreadsheet.
- Participants who received an incorrect formulation or meal, consumed <90% of meal or were non-compliance with OMP will be captured as an important protocol deviation.
- The spreadsheet will be reviewed prior to SDL to ensure all important deviations are captured.
- At the end of the study, IQVIA will convert this spreadsheet into a SAS dataset which will be provided to statistics and programming along with the other datasets.
- This dataset will be the basis for the summaries and listings of PDs.
- Important PDs (including deviations related to study inclusion/exclusion criteria, conduct of the trial, participant management or participant assessment) will be summarised and listed.
- A separate summary and listing of all inclusion/exclusion criteria deviations will also be provided. This summary will be based on data as recorded on the inclusion/exclusion page of the electronic case report form (eCRF).
- A Per Protocol Population will not be defined.

The following PDs will lead to exclusion from the pharmacokinetic parameter analysis outputs for the specific period (tables, statistical analysis and figures). Exclusions will be programmed by statistics and programming from the SDTM data:

- incorrect meal/formulation
- non-compliance with OMP (participants on treatments I, J, K – Section 5.1 Study Treatment Display Descriptors))
- consumed <90% of meal (in fed participants)

In addition, a participant may be excluded from the pharmacokinetic parameter analysis outputs for the specific period due to having an inadequate PK concentration profile. This will be determined by the Pharmacokineticist during an initial review of the PK concentration data prior to derivation of the PK parameters. In such cases, any data identified for exclusion will be provided to statistics and programming and flagged in the relevant Analysis Data Model (ADaM) datasets. This will be documented in the ADaM Data Reviewers Guide (ADRG).

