### 10.1. Sample Size Determination

The sample size is primarily based on feasibility. Approximately 60 participants will be enrolled in the study to obtain approximately 8 randomized participants (6 completers) in each group in Part A and approximately 12 randomized subjects (10 completers) in each group in Part B.

[figure not shown]
The within-subject variability for AUC(0-inf), AUC(0-t) and Cmax of danirixin [GSK Study 201037, GlaxoSmithKline Document Number [2015N248339\\_00](#)] was estimated to be 37.3%, 39.3% and 44.7%, respectively. Based upon the largest within-subject coefficient of variation (44.7% for Cmax of danirixin) and a sample size of 6 subjects completing each group in part A of the study, it is estimated that the half-width of the 90% confidence interval for the ratio of geometric means for the comparison of interest should be no more than 42% of the point estimates. Assuming an observed ratio of one, the corresponding 90% confidence interval for the ratio of geometric means would be 0.70 to 1.42.

A PK interim analysis is planned at the completion of Part A to select the formulation for evaluation in Part B.

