3.2. Final Analyses

The final planned study population, safety and PK concentration summaries will be performed after the completion of the following sequential steps:

1. All participants have completed the study as defined in the protocol.
2. All required database cleaning activities have been completed and final Source Data Lock (SDL) has been declared by data management (DM).
3. Study is unblinded
 - Randomization schedules are released in RANDALL NG and GSK create and quality control (QC) unblinded RANDALL dataset.
 - SMS2000 data is released in HARP
4. Unblinded RANDALL dataset and SMS2000 file are released to IQVIA by GSK via secure external alliance portal (EAP)
5. Study Data Tabulation Model (SDTM) data conversion has been completed by IQVIA including unblinding activities and QC of unblinded SDTM has been completed by DM.
6. Database freeze (DBF) on unblinded study population, safety and PC SDTM datasets has been declared by DM.

Following this, the PK parameter analyses will be performed after the PP SDTM domain is available.

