7.1.4. Strategy for Intercurrent Events

Participants who experienced the following intercurrent events will have data from the relevant treatment period excluded from analysis:

- Received incorrect formulation or meal
- Did not consume at least 90% of the meal (in fed participants)
- Did not provide an adequate PK concentration profile to allow reliable estimation of PK parameters

Inclusion of the participant's remaining data in the analysis effectively uses a missing at random assumption to account for the excluded data.

If a participant is included in the PK population but withdrew from the study prior to a treatment period, data for that and subsequent periods will not be imputed. Inclusion of the participant's data prior to withdrawal in the analysis effectively uses a missing at random assumption to account for the missing data.

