7.1.5.1. Statistical Methodology Specification

Endpoint / Variables

 Log-transformed AUC(0-inf) and Cmax in fed and fasted states. Log-transformed AUC(0-t), AUC(0-24) and t1/2 in fed and fasted states.
Model Specification

 Include all Part A data in the model. Mixed effects model with fixed effect terms for period and treatment (formulation and fed/fasted state). Participant will be treated as a random effect in the model. Point estimates on the \log_e scale for the least squares (LS) mean for each treatment and the LS mean difference between treatments (for comparisons specified in Section 7.1.2: Summary Measure), and associated 90% CI for the difference will be constructed using the residual variance. The LS means, LS mean differences and associated 90% CIs will then be back-transformed to obtain geometric LS mean for each treatment, and LS treatment ratios and associated 90% CIs. The Kenward and Roger method for approximating the denominator degrees of freedom and correcting for bias in the estimated variance-covariance of the fixed effects will be used.
Model Checking & Diagnostics

 Model assumptions will be applied, but appropriate adjustments maybe made based on the data. Distributional assumptions underlying the model used for analysis will be examined by obtaining a normal probability plot of the residuals and a plot of the residuals versus the fitted values (i.e. checking the normality assumption and constant variance assumption of the model respectively) to gain confidence that the model assumptions are reasonable. If there are any departures from the distributional assumptions, alternative models will be explored using appropriate transformed data.
Model Results Presentation

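### A whole PK period can be dropped as inadequate with no stated criterion, before the parameters at issue are derived, and with treatment not masked

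*SAP*

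**What the plan says.** SAP 7.1.4, and 7.2.4 for the secondary analyses, remove a treatment period for several intercurrent events. One is that the participant "Did not provide an adequate PK concentration profile to allow reliable estimation of PK parameters".

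SAP 10.1 (Appendix 1) separates this event from the rest. Wrong meal or formulation, a meal less than 90% eaten and omeprazole non-compliance are programmed from the study data. Inadequacy of the profile is left to one person: "This will be determined by the Pharmacokineticist during an initial review of the PK concentration data prior to derivation of the PK parameters". The exclusion applies to that period's PK parameter outputs as a whole. It is flagged in the analysis datasets and documented in the reviewer's guide.

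Protocol 7.4 makes the study open-label. SAP 3.2 lists release of the randomization schedules at step 3 and, at step 6, "Database freeze (DBF) on unblinded study population, safety and PC SDTM datasets has been declared by DM". The PK parameter analyses come after that. No section describes a review without treatment codes.

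SAP 7.1.1.2 builds AUC(0-inf) from AUC(0-t) plus the last concentration divided by the terminal rate constant. The terminal rate constant, its limits and the number of points are to be listed, with no acceptance limits. SAP 7.1.4 treats excluded periods as missing at random.

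**The concern.** Four features combine.

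- **No criterion.** Neither document sets a minimum number of samples, a rule for samples missed near the peak, or a limit on extrapolation, terminal points or fit.
- **Timing.** The test is whether parameters can be estimated reliably, yet it is applied before the terminal slope and the extrapolated area exist.
- **Scope.** The whole period goes, although Cmax does not depend on the terminal phase. In the other direction, a profile that passes the early look can yield an AUC(0-inf) that is mostly extrapolation, and no later step removes it.
- **No masking.** The judgement is made on the outcome data, and nothing keeps treatment from the person making it.

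At stake are the Part A ratios. SAP 3.1 makes the choice of formulation for Part B depend on relative bioavailability and between-participant variability, and dropping one unusual profile can move both. If removal depends on how the profile looks, the missing-at-random assumption is also strained.

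**Working it through.** **Inputs.** Protocol 10.1 gives the within-subject CV for AUC(0-inf), AUC(0-t) and Cmax, which "was estimated to be 37.3%, 39.3% and 44.7%, respectively". Precision is based on "a sample size of 6 subjects completing each group in part A of the study", with 8 randomized per group. Part B plans "approximately 12 randomized subjects (10 completers) in each group in Part B".

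**The plan's own figure.** The protocol says "the corresponding 90% confidence interval for the ratio of geometric means would be 0.70 to 1.42". The log-scale within-subject SD for Cmax is sqrt(ln(1 + 0.447²)) = 0.427. Then exp(2.015 × 0.427/√6) = 1.42, and its reciprocal is 0.70, so the figure reproduces with 5 degrees of freedom. It does so only with standard error SD/√n, which leaves out the factor √2 for a difference between two periods. The influence calculation below keeps that factor.

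**Worst case: the most extreme of n paired differences is dropped.**

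- SD of a paired log difference: √2 × 0.427 = 0.604 for Cmax. For AUC(0-inf), sqrt(ln(1 + 0.373²)) = 0.361, and √2 × 0.361 = 0.510.
- Shift in the mean log difference: E(n)/(n − 1) × SD, where E(n) is the expected maximum of n standard normal values: 1.267 for n = 6, 1.424 for n = 8, 1.539 for n = 10.

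| Parameter | n | Log shift | Factor |
|---|---|---|---|
| Cmax | 6 | 1.267/5 × 0.604 = 0.153 | 1.17 |
| Cmax | 8 | 1.424/7 × 0.604 = 0.123 | 1.13 |
| Cmax | 10 (Part B) | 1.539/9 × 0.604 = 0.103 | 1.11 |
| AUC(0-inf) | 6 | 1.267/5 × 0.510 = 0.129 | 1.14 |
| AUC(0-inf) | 8 | 1.424/7 × 0.510 = 0.104 | 1.11 |
| AUC(0-inf) | 10 (Part B) | 1.539/9 × 0.510 = 0.087 | 1.09 |

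The Part B rows assume the same CVs and a within-group comparison.

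**Against the precision.** With the factor √2 and 27 degrees of freedom for the pooled Part A model, the log half-width of the 90% interval is 1.703 × 0.604/√6 = 0.42. The Cmax shift is 0.153/0.42 = 0.36 of it.

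**Check in the SAP's model.** Dropping one period in the mixed model keeps the participant's other periods, so the paired calculation is an approximation. A leave-one-out simulation used the Part A sequences (6 completers per group, known variances, 4,000 runs) and assumed a between-subject CV of 30% or 60%, a figure that the documents do not give.

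- Cmax, randomly chosen period: median shift about 6%; 15% or more in 12 to 13% of drops.
- Cmax, most influential of the 12 periods behind a ratio: median 18 to 19%.
- AUC(0-inf), most influential period: median about 16%.

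**A period of fixed oddness.** In a balanced crossover one period has weight about 1/n in the log ratio. A period 2 SD out (an assumption) moves the Cmax ratio by exp(2 × 0.427/6) − 1 = 15.3% and AUC(0-inf) by exp(2 × 0.361/6) − 1 = 12.8%. At 1 and 3 SD the Cmax shifts are 7.4% and 23.8%. With 10 completers, as in Part B, the 2 SD shifts are 8.9% and 7.5%.

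**The case against.** Much can be said for the plan.

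- **Treatment known.** A reader might infer that the pharmacokineticist decides with the treatment codes in view. The documents do not say so. SAP 3.2 orders data release for the final analysis; it neither dates the initial review nor says what the reviewer sees. What stands is that treatment is not masked.
- **Odd profiles.** A reader might also infer that a real but unusual profile may be dropped for being unusual. SAP 10.7.2 handles outliers by a repeat analysis without them, and the test in 7.1.4 is reliable estimation. That is a fair distinction, but with no criterion nothing enforces it.
- **Early decision.** Deciding before derivation means that the reviewer has seen no AUC and no ratio. That is a real advantage, and it is why a later decision needs masking as well.
- **Second check.** SAP 7.1.1.2 flags parameters that cannot be determined, and the extrapolated share can be worked out from the listed AUC(0-inf) and AUC(0-t). So the information is recoverable. But the flag misses parameters that are calculable but poor, and nothing acts on the share.
- **Other limits may exist.** Derivation follows working practices that are not in the documents and may contain acceptance limits. The SAP does not bring them in.
- **Transparency.** Table 1.9, Listing 7, the concentration listing and individual plots would make a selective drop visible. They disclose it; they neither prevent it nor show its effect on the ratio.
- **Estimation only.** No hypothesis is tested. The estimates still inform the choice of formulation.

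**Conclusion.** The concern holds in this form: the adequacy exclusion has no stated criterion, precedes the parameters it is meant to protect, covers the whole period and is not masked to treatment. The change should be made before the data are reviewed.

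The factors of about 1.17 (Cmax) and 1.14 (AUC(0-inf)) are worst cases for Part A. They rest on 6 completers, the protocol's CVs read as within-subject values, approximately normal log differences, and removal of the most extreme one. If 44.7% were instead the CV of the difference itself, the Cmax factor would be exp(1.267/5 × 0.427) = 1.11.

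A reader might take 15 to 17% as the expected effect of an exclusion. It is not: a randomly chosen period moves the Cmax ratio by about 6%. The larger figures also belong to Cmax, whereas the timing problem concerns AUC(0-inf) and t1/2. They apply to Cmax because the whole period is removed. Nothing here shows that a selective exclusion was made or intended.

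**What to change.** Amend SAP 7.1.4, 7.2.4 and Appendix 1 as follows.

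1. Carry out the adequacy review on profiles stripped of treatment, sequence and period labels. Lock the exclusion list before codes are merged; for Part A, lock it before the interim analysis.
2. Decide exclusions per parameter after derivation, still without labels. Keep Cmax and AUC(0-t) when only the terminal phase is unreliable.
3. State acceptance limits for extrapolated area, number of terminal points and terminal fit. The documents give no basis for particular values; the sponsor should set them in advance.
4. Add percent extrapolated and the fit statistic to the listed parameters.
5. Report the ratios once more with the excluded periods restored, wherever the parameter can be calculated.

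The cost is SAP wording, a stripped dataset for the review step and one extra analysis run. No participant, visit or sample is added.

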10.2. Appendix 2: Schedule of Activities

10.2.1. Protocol Defined Schedule of Events

Schedule of Activities Part A (Group 1 and Group 2) and Part B (Group 1)

Periods 1-4

Procedure	Screening (up to 30 days prior to Day 1) ¹	Study Day (Treatment Periods 1-4) ²													Early Discontinuation /Follow-up (3 to 10 days post-last dose)	
		Day -1	1													
			Predose	0h	0.5h	1h	1.5h	2h	3h	4h	6h	8h	10h	12h	24h	
Informed Consent	X															
Inclusion and Exclusion Criteria	X	X														
Demographics	X															
Full Physical Exam including Height and Weight	X															
Brief Physical Exam		X														X
Medical History (includes substance usage)	X	X														

Procedure	Screening (up to 30 days prior to Day 1) ¹	Study Day (Treatment Periods 1-4) ²													Early Discontinuation /Follow-up (3 to 10 days post-last dose)	
		Day -1	1													
			Pre-dose	0h	0.5h	1h	1.5h	2h	3h	4h	6h	8h	10h	12h	24h	
Pregnancy Test, (WOCBP) ³	X	X														
FSH and estradiol (if needed)	X															
HIV, Hep B and Hep C Screen	X															
Urine Drug Screen	X	X														
Alcohol Screen-Breathalyzer	X	X														
Urine Cotinine Screen	X	X														
Admission to Unit		X														
Laboratory Assessments (include liver chemistries)	X	X														X
12-lead ECG ⁴	X	X						X								X

Procedure	Screening (up to 30 days prior to Day 1) ¹	Study Day (Treatment Periods 1-4) ²													Early Discontinuation /Follow-up (3 to 10 days post-last dose)		
		Day -1	1														
			Pre-dose	0h	0.5h	1h	1.5h	2h	3h	4h	6h	8h	10h	12h	24h		
Vital Signs ⁵	X		X												X	X	X
Randomization			X														
Meal ⁶			X														
Danirixin Administration ⁷				X													
Pharmacokinetic Sampling			X		X	X	X	X	X	X	X	X	X	X	X	X	
SAE Review																	
AE Review		X															
Concomitant Medication Review		X															
Discharge															X		

1. Screening must be performed within 30 days prior to receiving the dose of Danirixin on Day 1 of period 1.
2. Treatment periods 1-4 will include a minimum 5 day wash-out from day of dosing between each treatment
3. Serum pregnancy test (where applicable) will be performed at the screening visit and a urine pregnancy test at all other time points specified.

4. Triplicate ECGs at screening and on Day -1 of each treatment period only. Single ECGs at other timepoints (performed at a similar time of day as Day 1 Pre-dose), unless a reading meets the QTc stopping criteria, in which case two further measurements will be taken at the same time point and the average values captured.
5. Triplicate BP and HR at screening and pre-dose on Day 1 of each treatment period only. Single measurements at other timepoints (performed at a similar time of day as Day 1 Pre-dose). HR and BP assessments only performed at the 24 and 48 hr post dose and early discontinuation/follow-up visit timepoints.
6. Meal (where applicable) to be started and completed 30 minutes prior to of danirixin dosing. Meal to consist of 900-1000 calories and be composed of proper caloric content of protein/fat/carbohydrates per FDA guidance and participants will be required to consume at least 90% of meal.
7. When danirixin dosing occurs in the fasted state, participants will be provided with a light snack and then will fast from all food and drink (except water) from 10 hours prior to dosing until 4hrs post-dose on Day 1 in each treatment period at which time lunch will be provided. An evening meal will be provided at approximately 9 h post dose. At all other times during residency in the clinic, meals will be provided at appropriate times.

Part B – Group 2**Periods 1-3**

Procedure		Screening (Up to 30 days prior to Day 1) ¹	Qualification Visit Day -4 ⁹	Day -1	Study Day (Treatment Periods -1-3) ²												Early Discontinuation /Follow-up (3 to 10 days post-last dose)	
					Pre-dose	0h	0.5h	1h	1.5h	2h	3h	4h	6h	8h	10h	12h	24h	
Informed Consent	X																	
Inclusion and Exclusion	X		X															
Demographics	X																	
Full Physical Exam including Height and Weight	X																	
Brief Physical Exam			X															X
Medical History (includes	X		X															

Procedure	Screening (Up to 30 days prior to Day 1) ¹	Qualification Visit Day -4 ⁹	Day -1	Study Day (Treatment Periods -1-3) ²												Early Discontinuation /Follow-up (3 to 10 days post-last dose)	
				Pre-dose	0h	0.5h	1h	1.5h	2h	3h	4h	6h	8h	10h	12h	24h	
substance usage)																	
Pregnancy Test, ³ (WOCBP)	X	X	X														
FSH and estradiol (if needed)	X																
HIV, Hep B and Hep C Screen	X																
Urine Drug Screen	X	X	X														
Alcohol Screen-Breathalyzer	X	X	X														
Urine Cotinine Screen	X	X	X														
Admission to Unit			X														
Laboratory Assessments	X		X														X

Procedure	Screening (Up to 30 days prior to Day 1) ¹	Qualification Visit Day -4 ⁹	Day -1	Study Day (Treatment Periods -1-3) ²												Early Discontinuation /Follow-up (3 to 10 days post-last dose)	
				Pre-dose	0h	0.5h	1h	1.5h	2h	3h	4h	6h	8h	10h	12h	24h	
(include liver chemistries)																	
12-lead ECG ⁴	X		X						X								X
Vital Signs ⁵	X			X												X	X
Randomization				X													
Meal ⁶				X													
Danirixin Administration ⁷					X												
Omeprazole Administration ⁸		X	X		X											X	X
Diary Card completion for Omeprazole Dosing				←-----→													
Pharmacokinetic Sampling				X	X	X	X	X	X	X	X	X	X	X	X	X	

Procedure	Screening (Up to 30 days prior to Day 1) ¹	Qualification Visit Day -4 ⁹	Day -1	Study Day (Treatment Periods -1-3) ²												Early Discontinuation /Follow-up (3 to 10 days post-last dose)	
				Pre-dose	0h	0.5h	1h	1.5h	2h	3h	4h	6h	8h	10h	12h	24h	
SAE Review				←-----→													
AE Review			X		←-----→												
Concomitant Medication Review			X		←-----→												
Discharge																X	

1. Screening must be performed within 30 days prior to receiving the dose of Danirixin on Day 1 of period 1.
2. Treatment periods 1-3 will include a minimum 5 day wash-out from day of dose between each treatment.
3. Serum pregnancy test (where applicable) will be performed at the screening visit and a urine pregnancy test at all other time points specified.
4. Triplicate ECGs at screening and on Day -1 of each treatment period only. Single ECGs at other timepoints (performed at a similar time of day as Day 1 Pre-dose), unless a reading meets the QTc stopping criteria, in which case two further measurements will be taken at the same time point and the average values captured.
5. Triplicate BP and HR assessments at screening and pre-dose on Day 1 of each treatment period only. Single measurements at other timepoints (performed at a similar time of day as Day 1 Pre-dose). HR and BP assessments only performed at the 24 and 48 hr post dose and early discontinuation/follow-up visit timepoints.
6. Meal (where applicable) to be started and completed within 30 minutes prior to danirixin dosing. Normal and high fat meal will be described in the SRM.
7. When danirixin dosing occurs in the fasted state, participants will be provided with a light snack and then will fast from all food and drink (except water) from 10 hours prior to dose until 4 hr post-dose on Day 1 in each treatment period at which time lunch will be provided. An evening meal will be provided at approximately 9 h post dose. At all other times during residency in the clinic, meals will be provided at appropriate times.
8. OMP will be taken starting on Day -4 continuing daily through all treatment and washout periods until the day of the Period 3, 48hour PK assessment. The Day -4 Qualification visit only applies to period 1.

